The IDS pharmacy will oversee the pre-packaging of the study drug into 2-week AM/PM pill packs for patients to improve compliance with the study drug regimen, improve safety (so they take the right number of each type of medication pill), and facilitate delivery to patients on the day of their consent. The research staff or pharmacy will select study drug based on the randomization code that preserves blinding, place the patient's name and study ID in the drug accountability log and study database, and place it in the study box for that patient and arrange for the delivery.

Pill packs will be labeled with the study name and PI name, contact information about the study; and the names and doses of all potential study drugs.

4.7.1 Provision of study drug to patients:

Following randomization, study drug to participants in an expedited way (for example courier, overnight mail service).

4.8 Study Unblinding:

Each participating pharmacy team, or the central pharmacy, will hold the blind for their site. Each site will have 24-hour access to the blind. Each subject will be provided information as to whom to contact for unblinding information in the event of an emergency. There is one unblinded statistician with two unblinded supporting statisticians on the study team.

- 4.8.1 Multiple strategies will be developed to assure that study drug is stopped at the time of hospitalization (as metformin is typically stopped at hospitalization for safety reasons)
- 4.8.2 Multiple strategies will be developed to inform patients and their medical providers that they are in study involving metformin or fluvoxamine or ivermectin, and that it should be stopped prior to imaging studies with contrast.
- 4.8.3 Multiple strategies will be developed to inform patients' medical providers that they are in a study involving metformin or fluvoxamine or ivermectin, and thus any potential interacting medications, or metformin itself, should not be started while the patient is in the study. The patient may withdraw consent at any time.
- 4.9 Biosafety:

Patient samples will be carried in an expedited way (i.e. courier or mail services) in packaging that is approved for Biologic Substances Category B, UN 3373, per CDC guidelines for shipping SARS-CoV-2 samples: https://www.cdc.gov/coronavirus/2019-ncov/lab/lab-biosafety-guidelines.html#specimen

[figure not shown]

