  - Based on patient feedback, to reduce participant burden because SARS-CoV-2 symptoms may be present, we will offer the opportunity for patients to self-screen online to avoid burden and barriers to participating
    - This will be performed via a web-based form. Eligibility criteria and medical history will be by self-report entries into the secure web-based form.
    - After self-screening online, patients may elect to self-consent online, or have a consent discussion with an RC (section 5.4).
  - For patients who do not want to screen or consent via web-based form, screening and consent may be done over the phone with RC with eligibility criteria and history entered into the web-based form by the RC.
  - Patients will be asked to submit proof of their positive SARS-CoV-2 result via secure means, but the receipt of the result may occur after enrollment.
    - 5.3.1 GFR

GFR will be collected on persons > age 75 years or persons of any age who select or respond that they have chronic kidney disease, heart failure, or liver disease if a GFR is not available within 2 weeks in the EHR. It may be collected from patients by either self-collection kits sent to patients' homes with return arranged by the study team; or by local in-person collection.

Participants will receive the study drug at the same time as the GFR testing kit in the mail (or GFR drawn in person), as well as a return envelope for the study drug. They will start the study drug before their GFR result is returned. If the GFR result returns and is < 45ml/min, they will be asked to stop taking the study drug and return the remainder of the study drug. This will count as a screen failure.

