## 8.0 Withdrawal of Participants

8.1 Withdrawal Circumstances:

Participants may withdraw from the study at any time for any reason. Participants may be withdrawn from the study without their consent if at any point they develop an exclusion criteria that makes it unsafe for them to continue in the study. All data from patients withdrawn from the study will be analyzed up until time of withdraw. Clinical progression after withdrawal may be assessed via EHR or vital status review or by reaching out to patients or their contacts.

8.2 Withdrawal Procedures:

If patients choose to withdraw, study procedures including intervention and follow-ups will stop. Given the remote nature of this study, written notification is not required. If the patient chooses to withdraw, the study team will ask if the patient is willing to allow continued electronic medical record evaluation for the determination of study endpoints (partial withdrawal). We will also ask if the patient wishes to withdraw consent for the use of future biologic specimens. If the patient declines to participate in any component of research, no further study data will be collected, biologic samples will be destroyed, but existing study data may be used. Each of these circumstances will be documented and stored as a study document.

8.3 Termination Procedures:

Upon trial termination, study outcomes will be followed until completion. Case report forms and collection templates will be maintained in paper format (when applicable) and electronically for 7 years in accordance with regulations. Collected data will be used for secondary analyses with approval of the principal investigators in a deidentified fashion. Data entry will be completed, checked for accuracy, and locked for analysis within 1 year of enrollment of the final patient.

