## **12.0** Statistical Considerations

A detailed statistical analysis plan (SAP) will be included as an appendix and developed by the statisticians prior to analyzing unblinded data. The SAP may be amended as needed thereafter by the blinded statistician(s). All analyses will follow a modified intention to treat (mITT) approach, excluding participants who were screen failures or who did not ingest any study drug, unless specified otherwise.

12.1 Randomization:

Eligible and consenting participants who test positive will be enrolled and randomized evenly among the arms for which they are eligible, i.e. 1:1:1:1:1:1 for participants who are eligible for all 6 arms. Randomization will be stratified by study site from which their IP is dispensed. Stratum specific schedules will be preemptively generated using mass-weighted urn randomization with a total mass of  $\alpha = 6$ , which is a generalization of randomly permuted blocks that reduces predictability of future assignments. Patients eligible for one study drug and ineligible for another, who are still interested in the trial, may be randomized amongst the study drug arm for which they are eligible. Randomization schedules will be generated for each possible drug eligibility pattern, and assignments will be drawn sequential from each stratum specific sequence therein. Statistical analyses will be study drug specific and consist of all participants who were eligible for and randomized into the relevant arms. Direct comparisons of study drugs and evaluation of drug-drug interactions will be conducted amongst participants who were eligible for both drugs in the comparison/interaction.

12.2 Blinding:

Study drug will be prepared by an unblinded study pharmacy team. Study personnel and participants will be blinded to participant assignments and outcomes data for the duration of the study, excepting lab data as detailed below and situations that require the blind to be broken for safety reasons. These instances will be recorded and reported to the PI and DSMB. An unblinded analysis of the laboratory outcomes from the treatment cohort sub-study will be carried out by the unblinded statisticians and shared with the blinded investigators and potential sponsors of the trial.

12.3 Sample Size Assumptions:

The statistical design is for the comparison of metformin vs placebo, controlling for the effect of fluvoxamine and ivermectin.

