#### 12.4.1 Safety Monitoring:

Safety monitoring will be undertaken for each agent and combination. Regular reports will be provided to the DSMB at a mutually agreeable interval with an evaluation of safety outcomes that focus on comparisons of the frequency of deaths, SAEs and grade 4 events between the active treatment arms and placebo arm irrespective of attribution to study drug. Proportions and 95% exact confidence intervals will be used to summarize the results with unconditional exact tests and corresponding exact intervals to evaluate differences. Cumulative counts of adverse reactions and numbers of participants experiences and adverse reaction will be reported and compared similarly. Further safety assessments may be considered as demanded by the DSMB as well. The purpose of these reports is to catch any unexpected severe adverse reactions to metformin in the study populations. Formal statistical comparisons of safety endpoints using p-values will be undertaken at the request of the DSMB, and will otherwise not be reported.

12.4.2 Efficacy Monitoring:

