### UNIVERSITY OF MINNESOTA 08December2021 COVID-OUT (formerly called MET-COVID) (MET29324)

follow a modified intent to treat (mITT) principle, excluding participants who were postrandomization screen failures and who did not ingest any study drug. Formal comparisons will use 2-sided tests with a 5% significance level.

Descriptive statistics will be reported for baseline covariate information. Continuous variables will be summarized using mean and standard deviations, as well as median and interquartile range for skewed variables. Binary and categorical variables will be summarized using counts and percentages. Differences in important prognostic variables will be monitored visually with formal statistical testing undertaken only at the request of the DSMB.

Each study drug version control comparison will be separate. Each control group will consist of the participants who were eligible to receive the study drug but were assigned to a relevant placebo control arm instead. The metformin comparison will control for fluvoxamine and ivermectin use, and the fluvoxamine and ivermectin versus control comparisons will each control for metformin use. Primary hypotheses will be evaluated using logistic regression with a main effect for the relevant drug adjusted for study site and use of the other study drugs. The statistical significance of the main effect will be evaluated using a likelihood ratio test with interim monitoring boundaries specified above.

A secondary analysis for each study drug versus control comparison will control for age and BMI as well. Metformin effect heterogeneity with respect to biologic sex will be assessed in both cohorts though a logistic regression model with an interaction term, as well as separate logistic regression models fit to the data from males and females. During interim analyses, some participants will not have been followed adequately long for inclusion in the primary analysis. As a secondary analysis, marginal cumulative incidence rates in each arm at the specified follow-up interval will be estimated using the Kaplan-Meier method by censoring those in the midst of follow-up who have yet to experience the primary endpoint at their point of last study contact.

Laboratory outcomes, which are continuous longitudinally measured outcome, will be evaluated using generalized estimating equations with a treatment effect and adjustments for the corresponding outcome at baseline.

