13.2 Serious Adverse Event (SAE)

Serious adverse events will be collected from enrollment through day 14 and 28. Investigators will determine if the event is serious or related to the study drug.

An SAE is any AE that is:

- Fatal,
- life-threatening,
- requires or prolongs a hospital stay,
- results in persistent or significant disability or incapacity,
- a congenital anomaly or birth defect, or
- an important medical event\*.

\*Important medical events are those that may not be immediately life threatening, but are clearly of major clinical significance. They may jeopardize the subject, and may require intervention to prevent 1 of the other serious outcomes noted above. For example, drug overdose or abuse, a seizure that did not result in in-patient hospitalization, or intensive treatment of bronchospasm in an emergency department would typically be considered serious.

SAEs must be entered into the study database within 24 hours of investigator awareness of the event.

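### As written, randomised participants who took study drug before a GFR below 45 ml/min came back drop out of the between-arm safety comparisons

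*Protocol*

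**What the plan says.** Section 5.3.1 requires a GFR from people over 75, and from anyone reporting chronic kidney disease, heart failure or liver disease, if the health record has none from the last 2 weeks. For these people it says "They will start the study drug before their GFR result is returned". A result below 45 ml/min means they stop and send back the remaining drug, and "This will count as a screen failure". Section 4.7.1 places the dispatch of drug after allocation: "Following randomization, study drug to participants in an expedited way". A person in this position is therefore both randomised and exposed.

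Two places define the modified intention-to-treat set, and each applies its rule to all analyses:

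- Section 12.0: "excluding participants who were screen failures or who did not ingest any study drug, unless specified otherwise".
- Section 12.2 Data Analysis (the second section numbered 12.2): "excluding participants who were postrandomization screen failures and who did not ingest any study drug".

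Section 12.4.1 describes safety reports built on "comparisons of the frequency of deaths, SAEs and grade 4 events between the active treatment arms and placebo arm". It names no analysis population and makes no exception to 12.0. It gives the purpose of the reports as detecting unexpected severe reactions to metformin.

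Section 9.1 describes the GFR as obtained before enrolment, to make sure that these high-risk patients are above the limit.

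**The concern.** A modified intention-to-treat rule is normally written with efficacy in mind. Here it is stated as the default for everything, safety included, and one of its exclusion classes contains people who have taken study drug. Those people have kidney function below the trial's own limit, and section 9.1 ties the exclusion of renal failure to the risk of lactic acidosis on metformin. A safety comparison that omits them omits the exposed participants for whom that risk is of most interest.

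The second worry is reproducibility. Because 12.0 and 12.2 Data Analysis join the two exclusion conditions with different words, two statisticians working from the protocol could build different safety denominators.

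**Working it through.** There is no figure in the plan to reproduce, so the check applies each wording to each type of participant. Let S mean that the person is classed as a screen failure after randomisation, and N that the person took no study drug.

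- Section 12.0 excludes if S **or** N.
- Section 12.2 Data Analysis, read literally, excludes if S **and** N.
- Section 12.2 Data Analysis, read as a list of two excluded groups, excludes if S **or** N, the same as 12.0.

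| Participant | S | N | 12.0 | 12.2 literal | 12.2 as a list |
|---|---|---|---|---|---|
| Dosed, GFR below 45 | yes | no | out | in | out |
| Not a screen failure, never dosed | no | yes | out | in | out |
| Screen failure, never dosed | yes | yes | out | out | out |
| Not a screen failure, dosed | no | no | in | in | in |

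**Which reading of 12.2 is likelier?** The list reading. The literal one would keep an eligible person who never took a tablet, which defeats the purpose of modifying intention to treat. It would also leave the screen-failure exclusion with almost no work to do for the class that 5.3.1 creates, because those people are told to start drug before the result.

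**Consequence under the likelier reading.** Both sections exclude the dosed low-GFR participant from all analyses. The only way back in is the proviso at the end of the 12.0 rule, and 12.4.1 does not use it. The exclusion therefore carries into the safety comparisons.

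**Consequence under the literal reading.** For k dosed GFR failures, 12.0 counts 0 of k and 12.2 Data Analysis counts k of k.

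**How large is k?** The protocol gives no number. Two features point to a small one: known eGFR below 45 is already an exclusion in section 6.2, and a test is needed only where no recent result is on file. For participants eligible for all six arms, the 1:1:1:1:1:1 allocation puts 3 of 6, or half, of the affected people in arms containing metformin.

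**Would the data exist?** Section 13.2 states: "Serious adverse events will be collected from enrollment through day 14 and 28". Section 5.5 extends the health-record search to everyone enrolled, and 5.5.2 extends the vital-status search to everyone randomised. None of these is limited to the modified intention-to-treat set.

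**The case against.** The strongest reply has three parts.

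First, the difference between *or* and *and* is probably loose drafting in a section that calls itself brief. That stands. A reader might infer that 12.0 and 12.2 Data Analysis flatly contradict each other, but the text does not support this, because the natural reading of 12.2 gives the same two groups as 12.0. The wording is ambiguous, no more. The reply does not remove the point, however, since on that natural reading both sections drop the exposed participants.

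Second, safety populations are usually defined in the statistical analysis plan, which is not at hand and could supply the exception that 12.0 allows for. This also stands in part: the absence of a safety set from the protocol is no fault. What is open to criticism is that the protocol does state a rule, applies it to all analyses, and leaves it unmodified in the section describing the safety comparisons.

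Third, the safety consequence is limited. Serious events must be reported within 24 hours (13.6.1), the monitoring board receives near-timely reports of hospitalisations and deaths (14.2), and under 12.4.1 it can ask for further assessments. All of this stands. A reader might infer that harm in these participants would go unseen, and the protocol does not support that.

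It is also tempting to set 5.3.1 against section 8.1, which says of withdrawn participants "All data from patients withdrawn from the study will be analyzed up until time of withdraw". That is not an inconsistency. Section 8.1 includes people who develop an exclusion criterion during the study, whereas 5.3.1 concerns people found not to have met a baseline criterion, and treating the two differently is ordinary.

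**Conclusion.** The point holds as a minor one. Under the stated default, randomised participants who took study drug and then returned a GFR below 45 ml/min are left out of the arm-by-arm comparisons of deaths, serious adverse events and grade 4 events. The wording in 12.2 Data Analysis adds ambiguity but is not a firm contradiction.

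The size is k participants, unstated and probably small. The conclusion rests on two assumptions: that the screen-failure label in 5.3.1 carries the same meaning in section 12, and that no document outside the protocol already sets a different safety population. A reader might go on to infer biased efficacy estimates or lost power. Nothing in the protocol shows either, and neither is claimed.

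**What to change.** 1. In 12.4.1, state that the safety comparisons include every randomised participant who took at least one dose of study drug, GFR screen failures included, analysed by assigned arm with follow-up to Day 28.
2. Use one identical exclusion wording in 12.0 and 12.2 Data Analysis, saying explicitly whether screen failures who took drug are in or out of the modified intention-to-treat set.
3. Align the statement on GFR timing in 9.1 with the dose-before-result procedure in 5.3.1. This is a separate mismatch about eligibility timing, best corrected in the same amendment.

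The cost is one sentence and two wording changes. No new data collection is needed, because serious events, the health-record search and the vital-status search already cover these people as the sections read. The downside is that a few participants who stopped drug early enter the safety set, which slightly dilutes average exposure in it.

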#### Optional serum samples

Serum samples (approximately 20-30cc) will be collected on patients who are willing to provide these samples, via mobile phlebotomy to their home, to better understand treatment response and mechanism. A random sample of 95% of these samples will be analyzed. Labs will be processed at local eligible labs, or at the University of Minnesota Advanced Research and Diagnostic Laboratory, which is a CLIA-certified, CAP-accredited clinical testing laboratory that is certified to receive, process and test samples from COVID-19 patients. Any antibody samples will be conducted by FDA-approved assays or academic institutions that have validated their assays.

#### 5.4 Informed Consent

Consent will be obtained (via self-consent (below), or a traditional consent conversation) before beginning any study procedures. The entire consent document will be reviewed, including all study procedures and expectations, risks, benefits, and what volunteering means. Participants will be asked questions to gauge their level of understanding.

Potential participants will be given time to read the consent and ask questions. If needed, a participant may take additional time to review the consent or discuss participating in the study with family/friends. The consent conversation will be done remotely, using a phone or secure HIPAA compliant video/web conferencing or in-person.

Based on patient feedback, we will also offer the opportunity to self-consent online, waiving the consent conversation. This would mean that after potential participants answer eligibility questions with the RC or online (section 5.3 above), they could access the online consent module.

- Patients will be able to read the consent form online and asked to answer comprehension questions about the consent. Participants will review short sections and need to click in order to move to the next section to increase engagement and comprehension of the study during the self-consent process.
- If their responses to the comprehension questions indicate that they are wellinformed about the study, they would be able to sign the consent form online.
- If their responses indicate that they lack understanding, the RC may call them for a traditional consent conversation and assessment of comprehension.

The consent document will be presented to the participant as an electronic document (eConsent) through the University of Minnesota's instance of REDCap. The REDCap eConsent document will contain the full consent text and is compliant with FDA 21 CFR Part 11 for the electronic capture of signatures. Participants will be sent a link via email or text to the REDCap survey which will contain the full consent text. After signing the consent, participants will receive an electronic copy of the signed document or a paper copy if in-person. Consent may also be done in person via hard-copy print out of the consent form if patients are in clinic for other reasons.

5.4.1 Non-English Speaking Participants:

Non-English speaking patients will not be specifically targeted for enrollment, but any non-English speaking participants will be consented using the short form consent process.

Before consenting, the study team will ensure that a suitable interpreter will be available during the consent process and throughout the study. For any non-English speakers who are enrolled using the short form consent process, a certified translation will then be obtained for the long form consent form in the participant's preferred language. After the IRB approves this document, the participant will be re-consented using the translated form.

